¹⁸ PK blood samples will be collected in the clinic 1 to 4 hours after at home IP application by the subject.

¹⁹ Subject will be randomized using the IWRS.

²⁰ During any wash out and screening periods, any changes in the health of subjects should be recorded as changes in medical history unless an event occurred as a result of a study-related procedure and is unanticipated; in such cases, the event should be recorded as an AE and reported to the Institutional Review Board (IRB) as an "unanticipated problem" in accordance with local procedures.

ABBREVIATIONS

AE	Adverse Event
AGA	Androgenetic Alopecia
ALT	Alanine Aminotransferase
ANCOVA	Analysis of Covariance
AST	Aspartate Aminotransferase
BMI	Body Mass Index
BUN	Blood Urea Nitrogen
CFR	Code of Federal Regulations
CK-MB	Creatine Kinase-MB
COVID	Coronavirus Disease
CTCAE	Common Terminology Criteria for Adverse Events
ECG	Electrocardiogram
eCRF	Electronic Case Report Form
EDC	Electronic Data Capture
EOS	End of Study
EOT	End of Treatment
FDA	Food and Drug Administration
GGT	Gamma-Glutamyltransferase
HBsAg	Hepatitis B surface Antigen
HGA	Hair Growth Assessment
HGI	Hair Growth Index
HIV	Human Immunodeficiency Virus
Hr	Hairless
IB	Investigator's Brochure
ICE	Intercurrent Event
I/E	Inclusion/Exclusion
IGA	Investigator's Global Assessment
IND	Investigational New Drug
IP	Investigational Product
IRB	Institutional Review Board
ITT	Intent-to-Treat
IUD	Intrauterine Device
IWRS	Interactive Web Response System
LDH	Lactate Dehydrogenase
LSM	Least Squares Means
LSR	Local Skin Reaction
MCH	Mean Corpuscular Hemoglobin
MCHC	Mean Corpuscular Hemoglobin Concentration
MCV	Mean Corpuscular Volume
MedDRA	Medical Dictionary for Regulatory Activities
mL	Milliliter
OTC	Over-the-Counter

PD	Pharmacodynamics
pg	Picogram
PK	Pharmacokinetics
PP	Per-Protocol
PRP	Platelet Rich Plasma
PT	Preferred Term
RBC	Red Blood Cells
RDW	Red Blood Cell Distribution Width
SAE	Serious Adverse Event
SGOT	Serum Glutamic Oxaloacetic Transaminase
SGPT	Serum Glutamic Pyruvic Transaminase
SOC	System Organ Class
SOE	Schedule of Events
SSA	Subject Self-Assessment
T3	Triiodothyronine
T4	Thyroxine
TAHC	Target Area Hair Count
TAHD	Target Area Hair Darkness
TAHW	Target Area Hair Width
TI	Therapeutics, Incorporated
TR	Thyroid Hormone Receptors
TSH	Thyroid Stimulating Hormone
WBC	White Blood Cells
WHO	World Health Organization

TABLE OF CONTENTS

Protocol Approval.....	2
Study Acknowledgement.....	3
Protocol Synopsis.....	4
Schedule of Events.....	15

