Treatment Groups	After enrollment in the study, each subject will be randomized (1:1:1) to 1 of the 3 IPs listed above. The assigned IP will be applied once daily (1 mL/dose of IP) for 16 weeks, with application to the scalp focusing on the regions that are bald and thinning.
Duration of Treatment	16 weeks
Duration of Study	Approximately 26 weeks for an individual subject (6 weeks [45days] for screening, 16 weeks for treatment, and 4 weeks for follow-up).
Study Population	Male subjects 18-55 years of age with mild to moderate AGA
Total Number of Subjects	Approximately 72 subjects will be enrolled (24 per treatment group)
Number of Sites	Approximately 12 sites will participate in the study
Inclusion Criteria	To enter the study, a subject must meet the following criteria: 
1. Subject is male, 18-55 years old.2. Subject has provided written informed consent.3. Subject has a clinical diagnosis of mild to moderate AGA in temple and vertex region with a score of IIIv, IV, or V on the Modified Norwood-Hamilton Scale.4. Subject, in the investigator's opinion, is in good general health and free of any disease state or physical condition that might impair evaluation of AGA or exposes the subject to an unacceptable risk by study participation.

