--	--

³ Macro photo shoots must occur within 7 days after the Baseline visit if a re-shoot is required.

	
Visits 5 and 7 (Days 42 ± 3 and 70 ± 3): Week 6 and Week 10 Phone Calls. The site staff will contact the subject by telephone and query the subject for any changes in health status. The site staff will remind the subject to continue to apply the IP every morning until the next clinic visit and to record all applications in the Subject Diary. Any AEs will be discussed with the investigator to determine if the subject should return to the study site for an unscheduled visit. The next visit will be confirmed.
 
Visits 8 and 9 (Days 84 ± 3 and 112 ± 3): Week 12 and Week 16/End of Treatment (EOT) or Early Termination. Note: Visits should be scheduled so that PK sample collection will occur 1 to 4 hours after the subject has self-applied the IP application at home. The subject will return to the clinic and be queried for any changes in health status since the previous visit, including concomitant medications and concurrent procedures/therapies. A physical examination, vital signs (with height and weight at Visit 9 only), and 12-lead ECG will be performed. Blood and urine will be collected for clinical laboratory testing (chemistry [with lipid panel and thyroid function], hematology, urinalysis, and cardiac biomarkers) and a PK blood sample will be collected 1 to 4 hours after IP application. Global photos will be taken. SSAs will be performed. IGA and LSRs will be assessed. The scalp micro-dot tattoo will be checked and re-applied if needed; then, macro photographs will be taken. IP accountability will be documented; all containers of IP and Subject Diaries will be collected and reviewed. At Visit 8 only, additional IP and a new Subject Diary will be dispensed. Any AEs will be recorded. The next visit will be confirmed.
 
Visit 10 (Day 140 ± 5): Week 20/End of Study (EOS). The subject will return to the clinic and be queried for any changes in health status since the previous visit, including concomitant medications and concurrent procedures/therapies. If any new or worsening clinically significant abnormalities were present at EOT, or as warranted based on the subject's current medical condition, any of the following assessments may be performed: a physical examination, vital signs, 12-lead ECG, and clinical laboratory testing (chemistry [with lipid panel and thyroid function], hematology, urinalysis, and cardiac biomarkers). LSRs will be assessed. AEs will be recorded. The subject will exit the study.

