	
application. The evaluator will assess the subject's scalp hair growth using the following 7-point scale: greatly decreased (-3), moderately decreased (-2), slightly decreased (-1), no change (0), slightly increased (1), moderately increased (2), and greatly increased (3).
 
Quantitative Hair Measurements
 
TAHC, TAHW, and TAHD will be calculated using digital image analysis from standardized macro photos. TAHC, TAHW, and TAHD will be calculated for non-vellus and vellus/vellus-like (miniaturized) hair, separately.
 
Subject Self-Assessment Questionnaires
 
The subject will use the standardized global photos (i.e., a vertex view and a superior view) of the subject's scalp taken at Visit 1/Screening and will compare them to the current visit's photos of subject's scalp hair growth for the following 2 assessments, which comprise the SSA:
 
• Hair Growth Assessment (HGA) [1]. Scalp hair growth will be compared from Baseline using the following 7-point scale: greatly decreased (-3), moderately decreased (-2), slightly decreased (-1), no change (0), slightly increased (1), moderately increased (2), and greatly increased (3)• Hair Growth Index (HGI) [2]. Scalp hair growth will be compared from Baseline using the following 7-point scale: much less (-3), moderately less (-2), slightly less (-1), the same amount (0), slightly more (1), moderately more (2), and much more (3) for the following 3 questions:
1. “Since the start of treatment, when I look at my thinning area, I can see ... (scalp)”;2. “Since the start of treatment, my hair now covers ... (scalp)”;3. “Since the start of treatment, the appearance (thickness/quality/amount) of the thinning area on my head is ...” 
Safety:
 
Physical examinations, vital signs, 12-lead ECGs, clinical labs (chemistry [including lipid panel and thyroid function], hematology, urinalysis, and cardiac biomarkers), LSRs, and AEs will be recorded per the SOE.
 
LSRs of erythema, edema, erosion, scaling, pruritus, and burning/stinging will be assessed using a 5-point ordinal scale (0=none, 1=minimal, 2=mild, 3=moderate, and 4=severe). Only reactions that require medical intervention (e.g., prescription medication) will be documented as AEs. Any reactions to the IP that are not listed above will be recorded as AEs.
 
Pharmacokinetics:
 
At Visit 2, subjects will be dosed in the clinic and a PK blood sample will be collected before the first dose as well as 1-4 hours post-dose. At visits 4, 6, 8, and 9, PK blood samples will be collected. These visits should be scheduled so that PK sample collection will occur 1 to 4 hours after the subject has self-applied the IP application at home.

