Study Endpoints	
Primary Efficacy Endpoint(s):
 
1. Changes from Baseline in non-vellus TAHC using digital image analysis at Week 16.2. The subject's evaluation of treatment benefit via the HGA questionnaire at Week 16.

	
Secondary Efficacy Endpoints:
 
1. Changes from Baseline in non-vellus TAHW using digital image analysis at Week 16.2. Changes from Baseline in non-vellus TAHD using digital image analysis at Week 16.3. The subject's evaluation of treatment benefit via the HGI questionnaire at Week 16.4. Proportion of subjects with each IGA grade at Week 16. 
Safety Endpoint(s):
 
1. Incidence (severity and causality) of any local and systemic AEs.2. Number of subjects with presence (and severity) of the following LSRs: erythema, edema, erosion, scaling, pruritus, and burning/stinging at each time point.3. Changes from Baseline in vital signs at each time point.4. Changes from Baseline in clinical laboratory tests (chemistry [including lipid panel and thyroid function], hematology, and urinalysis, and cardiac biomarkers) at Week 4, Week 8, Week 12, and Week 16.5. Changes from Baseline in ECG parameters and overall ECG interpretation at Week 4, Week 8, Week 12, and Week 16. 
Pharmacokinetics Endpoint(s): If plasma concentrations of TDM-105795 are quantifiable, the plasma concentrations will be summarized for active treatment groups.

Sample Size Calculations	The sample size for this study is based on clinical considerations only. No formal sample size calculation was performed.

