8.5 Sample Size

The sample size for this study is based on clinical considerations only. No formal sample size calculation was performed.

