8.9 Safety Evaluation

Summaries of the safety parameters will be provided as described below for the Safety population. No inferential analyses are planned.

8.9.1 *Extent of Exposure*

Descriptive statistics will be used to summarize the extent of exposure in the Safety population.

The duration of treatment for a subject will be calculated as the date of final application minus date of first application plus 1.

The total amount of IP used for a subject will be calculated as the difference between the weight of the IP dispensed and weight of IP returned. For the calculation of total amount of IP used, if test article is not returned at a given collection period, the amount of IP used for that period will be unknown and treated as missing.

The mean daily amount of IP applied for a subject will be calculated as the total amount of IP applied divided by the duration of treatment will be calculated.

8.9.2 *Vital Signs*

Descriptive statistics will be provided for the observed and change from Baseline values for temperature, systolic and diastolic blood pressure, heart rate, respiration rate, height, weight, and BMI for each treatment group.

8.9.3 *Local Skin Reactions*

LSRs (erythema, edema, erosion, scaling, pruritus, and burning/stinging) will be summarized by frequency and severity of each individual LSR for each treatment group.

8.9.4 *Electrocardiograms*

Descriptive statistics will be provided for the observed and change from Baseline values for ECG parameters by treatment group. Changes in overall interpretation of the ECG from Baseline to Weeks 4, 8, 12, and 16 will be examined by shift table.

8.9.5 *Clinical Laboratory Tests*

Clinical laboratory tests will be evaluated for any material changes during the study period. All laboratory data (chemistry [including lipid panel and thyroid function], hematology, urinalysis, and cardiac biomarkers [CK-MB, Troponin T, and NT-proBNP]) will be listed and reported in the units received from the laboratory. Shift tables by analyte and by out of range flag will be presented to facilitate the evaluation of change from Baseline to Weeks 4, 8, 12, and 16.

8.9.6 *Adverse Events*

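### The SAP specifies no any-time or worst post-baseline summary for local skin reactions, laboratory tests or ECG interpretation, and no rule for off-schedule safety values

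*Protocol*

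**What the plan says.** **Skin reactions.** Safety endpoint 2 (Protocol synopsis and 17.3.2, SAP 3.3) is the "Number of subjects with presence (and severity) of the following LSRs: erythema, edema, erosion, scaling, pruritus, and burning/stinging at each time point". SAP 8.9.3 says only that the six reactions "will be summarized by frequency and severity of each individual LSR for each treatment group". It does not say whether that is by visit, overall or by worst grade. Protocol 10.4.4 limits which reactions become adverse events (AEs): "Only reactions that require medical intervention (e.g., prescription medication) will be documented as AEs".

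**Laboratory tests and ECG.** Safety endpoints 4 and 5 name Weeks 4, 8, 12 and 16. SAP 8.9.5 offers laboratory shift tables for the "evaluation of change from Baseline to Weeks 4, 8, 12, and 16", and SAP 8.9.4 gives the ECG interpretation a shift table to the same weeks. The ECG parameter statistics in 8.9.4 name no visits. All laboratory data are also listed.

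**Per-subject counting.** SAP 8.9.6 counts a subject once within a preferred term or system organ class, and summarises maximum severity, for AEs only.

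**Off-schedule values.** AEs raised at the Week 6 and Week 10 calls go to the investigator to "determine if the subject should return to the study site for an unscheduled visit". Week 20 laboratory tests and ECGs are conditional (Schedule of Events, footnote 3). Early termination shares the Visit 9 column (footnote 1). The visit windows in SAP 8.8.2.1 apply to hair counts, width and darkness, the two subject questionnaires and the investigator's global assessment. No safety measure is included.

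**The concern.** Safety and tolerability is the second study objective, and the analysis is descriptive with about 24 men per arm. The natural tolerability figure is the share of men in each arm who had a given reaction at any time, by worst grade. For laboratory tests and ECG it is the share who went out of range, or whose interpretation worsened, at any time on study.

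A series of by-visit counts does not give that figure. The counts cannot be added, because they do not show whether the same men or different men are affected each time. Two arms with identical by-visit tables can differ widely in the number of men ever affected.

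The silence on off-schedule records adds to this. Week 20 laboratory tests and ECGs are taken mainly in men with a recent abnormality or a clinical reason, yet Week 20 is outside the shift tables. So are values from unscheduled visits. Safety values from a man who leaves early have no stated assignment beyond the shared Visit 9 column. If these choices are not fixed in the SAP, they may be made after the data have been seen.

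**Working it through.** **No plan figure to reproduce.** The documents state no incidence or precision target on this point, and SAP 8.5 says "No formal sample size calculation was performed". The only stated arithmetic is 3 arms × 24 = 72, which agrees.

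**Inputs**
- n = 24 men per arm (Protocol synopsis).
- k = 6 post-baseline skin-reaction visits: Weeks 2, 4, 8, 12, 16 and 20 (Schedule of Events).
- k = 4 visits in the laboratory and ECG-interpretation shift tables: Weeks 4, 8, 12 and 16.
- c = number of men affected at each visit. The documents give no value, so c = 1, 2 and 3 are assumptions.

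**Formulas.** With c men affected at every visit, the number ever affected is
- at least c (the same men each time);
- at most min(24, c × k) (different men each time);
- 24 × [1 − (1 − c/24)^k] on average if visits were independent.

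**Skin reactions, k = 6**

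| c per visit | Minimum ever | Maximum ever | If independent |
|---|---|---|---|
| 1 (4.2%) | 1 (4.2%) | 6 (25%) | 22.5%, 5.4 men |
| 2 (8.3%) | 2 (8.3%) | 12 (50%) | 1 − (22/24)^6 = 40.7%, 9.8 men |
| 3 (12.5%) | 3 (12.5%) | 18 (75%) | 55.1%, 13.2 men |

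**One analyte or the ECG interpretation, k = 4**

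| c per visit | Minimum ever | Maximum ever | If independent |
|---|---|---|---|
| 1 (4.2%) | 1 (4.2%) | 4 (16.7%) | 15.7%, 3.8 men |
| 2 (8.3%) | 2 (8.3%) | 8 (33.3%) | 1 − (22/24)^4 = 29.4%, 7.1 men |
| 3 (12.5%) | 3 (12.5%) | 12 (50%) | 41.4%, 9.9 men |

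The maximum is c × k and the minimum is c, so the ratio between them is 6 for skin reactions and 4 for the shift tables at each c shown.

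**Which results the AE tables already count once per subject**

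| Result | Route to a per-subject count |
|---|---|
| New or worsening, clinically significant laboratory result | AE (Protocol 12.1, SAP 7.6) |
| Laboratory finding within the CTCAE Grade 2 and AE wording | AE (Protocol 14.4) |
| New or worsening, clinically significant ECG result | AE (Protocol 10.4.3) |
| Listed skin reaction needing medical intervention | AE (Protocol 10.4.4) |
| Listed skin reaction not needing intervention, at any grade | None specified |
| Out-of-range laboratory value or abnormal ECG not recorded as an AE | None specified |

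The last two rows are the gap. By the wording of 10.4.4, even a reaction scored severe stays out of the AE tables if it needs no intervention.

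**The case against.** The case against has five parts.

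- **The AE tables cover the important events.** This stands for clinically significant laboratory and ECG changes and for reactions needing intervention, whichever visit found them. A reader might infer that abnormal thyroid, cardiac or ECG results found between visits drop out of the comparison of arms. For clinically significant results the documents do not support that.
- **The SAP does not rule out the missing tables.** SAP 8.9.3 and the ECG parameter statistics name no visits. A reader might infer that everything is planned strictly by scheduled visit, that ever-affected counts will never be produced, or that unscheduled values will enter no table at all. These go beyond the text. Only the shift tables are explicitly limited to named weeks; elsewhere exclusion would be an inference from silence. The phone-visit text also does not say that laboratory tests or ECGs are taken at an unscheduled visit.
- **The data are recoverable.** SAP 8.2 generally supports tables with listings, SAP 8.9.5 lists all laboratory data, and SAP 8.4 permits further analyses if identified as unplanned. This is correct, but a count assembled by hand or labelled post hoc is weaker than a prespecified table.
- **The numbers are hypothetical.** They are. The maximum needs non-overlapping sets of men at every visit, and the earlier single-dose study reported no skin reactions. The illustration shows what the tables cannot distinguish; it does not forecast a rate.
- **Worst value is undefined for analytes that can move either way, and fasting status varies.** The first is met by tabulating low and high separately. The second affects the planned by-visit tables equally.

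**Conclusion.** The point holds as a gap in specification. SAP 8.9.3 to 8.9.5 and safety endpoints 2, 4 and 5 plan no any-time or worst post-baseline summary for skin reactions, laboratory tests or ECG interpretation. Unscheduled and Week 20 laboratory and ECG values fall outside the shift tables, and no assignment rule covers safety data.

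The gap is confined to reactions not needing intervention and to out-of-range or abnormal results not recorded as AEs. For these, at an assumed 2 of 24 per visit, the planned counts cannot separate 8% from 50% of men ever affected by a skin reaction, or 8% from 33% for an analyte or the ECG interpretation. The per-visit count is an assumption; the ambiguity also appears at 1 and 3 of 24. It disappears only if the reported counts happen to fix who is affected, for example when just one visit has any cases.

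No sample size, efficacy result or stated figure changes. In a descriptive phase 2 study this is a worthwhile, low-cost improvement to the main tolerability output.

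**What to change.** Amend SAP 8.9.3 to 8.9.5 only, for the Safety population by arm, and keep the by-visit tables:

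1. **Skin reactions.** For each of the six, give the number and percent of subjects by worst post-baseline severity, and the number whose worst score exceeds their Baseline score.
2. **Laboratory tests.** For each analyte, tabulate the shift from Baseline to the worst post-baseline out-of-range flag, with low and high directions separate.
3. **ECG.** Tabulate the shift from Baseline to the worst post-baseline overall interpretation.
4. **Records used.** State that these summaries take all post-baseline records, including unscheduled, early-termination and Week 20 values.

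The protocol endpoints can stay as they are, so no protocol amendment is needed. The cost is a few extra tables from data already collected. The any-time skin-reaction percentages will tend to look higher than the by-visit ones, so a table note should say that each subject is counted once at his worst grade over the study.

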1. BACKGROUND

The skin, the largest body organ, is well recognized as a target for thyroid hormones. The biological activities of thyroid hormone (T3) are mediated through nuclear thyroid hormone receptors (TR). These effects are in part mediated through ligand-specific interactions of TR with its partner retinoid X receptor and binding of these transcription factors to specific promoter regions of thyroid hormone response element genes. Two highly homologous TRs, designated as TR α and TR β , are present in the skin. Expression of TR α and TR β has been localized to nuclei of outer root sheath and dermal papilla cells in human hair follicles, suggesting a role(s) of thyroid hormones in hair growth [3, 4].

Immunohistochemistry staining of TR in human scalp hair follicles shows TR β 1 protein is predominantly present in scalp hair follicles [3]. Thyroid hormone also stimulates extracellular matrix production such as proteoglycan and glycosaminoglycan synthesis by dermal fibroblasts [5]. In humans, changes in the texture of the hair, as well as alopecia of the scalp, the eyebrow, and other body hair are some characteristic clinical signs of myxedema. Hypothyroidism causes alopecia characterized by dull, brittle hair and an increase in the percentage of follicles in telogen. In addition, treatment of thyrotoxicosis (Graves' disease) led to reversible alopecia [6].

The hair cycle is a highly regulated process, consisting of four distinct phases: anagen (growing phase), catagen (regressing phase), telogen (resting phase), and exogen (shedding phase). In the initiation of each cycle, stem cells in the bulge divide and migrate downward to enter anagen phase of hair cycle directed by the dermal papilla. Hormones including T3 are important modulators of this process through their interactions with complex, genetically determined biological pathways [7]. Canonical Wnt signaling pathway has been implicated to play a central role in hair follicle development and morphogenesis. Genetic analysis has also identified mutation at Hairless (Hr) gene and this genetic change is associated with congenital hair loss disorders [8]. Thyroid receptors interact with hairless gene product (Hr), a transcription factor required for hair growth [9, 10]. However, precise roles of TR in the regulation of hair growth and associated co-regulators are largely unknown.

Thyroid hormone receptor agonists (thyromimetics) are closely associated with hair growth [11]. In animals, thyroid hormones have been shown to stimulate epidermal proliferation and hair growth. Topical triiodothyronine (T3) stimulates epidermal proliferation, dermal thickening, and hair growth in both mice and rats. Some human subjects given thyroxine (T4) to treat thyroid hormone deficiency reported hair growth as a side effect [11]. Thyroid hormones are also found to directly alter human hair follicle functions including anagen prolongation and stimulation of both hair matrix keratinocyte proliferation and hair pigmentation [11]. In 2009, Li et al reported a TR- β subtype-selective thyromimetic PF-00277343 that is efficacious in both mouse and monkey hair growth models after topical applications [12]. They reported that the serum drug level of PF-00277343 is below the limit of quantification during tests in the bald stump-tailed macaques (*M. arctoides*) after successive application of the drug for 3 months in the monkeys [12]. Recently, Contreras-Jurado et al showed that deletion in mice of the thyroid hormone nuclear receptors TR α 1

and TR β (the main thyroid hormone–binding isoforms) results in impaired epidermal proliferation, hair growth, and wound healing [13]. Stem cells located at the bulge of the hair follicles are responsible for hair cycling and contribute to the regeneration of the new epidermis after wounding. They also demonstrated that thyroid hormone signaling is an important determinant of the mobilization of stem cells out of their niche in the hair bulge [13]. In 2016, a thyromimetic compound KB2115 was shown to significantly increase the percentage of anagen hair follicles compared with vehicle controls in *in vitro* cultured human scalp hair follicles [14]. KB2115 significantly increased the percentage of proliferating Ki67-labeling cells in the hair matrix, whereas the percentage of apoptotic (TUNEL) hair matrix cells remained unchanged, suggesting prolongation of anagen phase by KB2115. KB2115 effectively countered the tendency of organ-cultured hair follicles to spontaneously enter into catagen [14]. Altogether, these studies indicated that thyromimetics may prevent or reduce premature catagen entry leading to telogen effluvium *in vivo*, and promote anagen entry and hair growth. However, due to systemic toxicity concerns of thyromimetics, no thyromimetics have been tested in the clinic for treating androgenetic alopecia (AGA).

To date, only two drugs, minoxidil (Rogaine, a potassium channel opener) and finasteride (Propecia, a 5a-reductase inhibitor), have been approved for treating AGA by the FDA. Current treatments such as minoxidil and finasteride are only efficacious in a small percentage of subjects, apart from drug-related undesirable side effects. Therefore, significant unmet medical need exists in developing more efficacious drugs with less drug-related unwanted side effects for treating AGA, and other forms of hair loss. Drugs with novel mechanisms may lead to robust efficacy and superior safety for the treatment of AGA.

The Sponsor is exploring the use of thyromimetics for treating AGA with a suitable topical drug candidate for potential clinical application. The Sponsor has developed TDM-105795 topical solution for the potential treatment of AGA. TDM-105795 is a thyroid hormone receptor-beta agonist being developed as a topical drug to promote hair growth. Preclinical assessment of TDM-105795 indicated that TDM-105795 has poor systemic absorption following topical application and short elimination half-life to avoid unwanted systemic effects. Moreover, an *in vivo* efficacy study in C3H mice suggests that TDM-105795 was able to potently stimulate hair growth in telogen follicles in a dose-dependent manner when applied topically. This is likely because TDM-105795 is able to induce a premature initiation of anagen in telogen hair follicles when binding to thyroid receptors in hair follicle cells. No overt abnormality was observed associated with the treatment. TDM-105795 therefore has a potential to be a novel, potent, and safe therapy to promote hair growth in AGA.

One first-in-man, single ascending dose pharmacokinetic (PK) study was conducted with TDM-105795 (Study 239-11651-101). In this study, 30 male subjects with moderate to severe AGA were studied; subjects received a single dose of 0.025 mg (N=8), 0.05 mg (N=8), 0.1 mg (N=8), or placebo (N=6) applied to the scalp in the hair loss area (e.g., top of head and temple regions) and had PK blood draws at pre-dose and 0.5, 1, 1.5, 2, 3, 4, 5, 6, 8, 10, 12, 24, and 48 hours after the dose. No measurable plasma drug levels were detected in any samples for any subjects (below the limit of quantification of 5 pg/mL). There were no adverse events (AEs) and no local skin reactions

(LSRs) of erythema, edema, erosion, scaling, pruritus, and burning/stinging for all subjects across all visits. There were no materially clinically significant changes in vital signs, clinical laboratory tests (including thyroid function), and electrocardiograms (ECGs).

A multi-dose PK study with TDM-105795 (Study 239-11651-102) was recently completed. In this study, 32 male subjects with moderate to severe AGA were enrolled. Subjects received 1 mL of TDM-105795 topical solutions (0.0025%, 0.005%, 0.01%, or 0.02%) or placebo for once daily application for 4 weeks. Results showed that the doses tested were well tolerated. There were no material clinically significant changes in vital signs, clinical laboratory tests (including thyroid function), ECGs, echocardiograms, and cardiac biomarkers. In addition, there were no consistently measurable plasma drug levels above the lower limit of quantification (5 pg/mL). Based upon these findings, TDM-105795 formulation strengths of 0.0025% and 0.02% were chosen for further evaluation in the current Proof-of-Concept study.

